### 2.5.1.4 Vital signs

Analysis of the vital sign measurements using summary statistics for the change from baseline for each post-baseline visit will be performed. These descriptive summaries will be presented by vital sign, and visit/time. Change from baseline will only be summarized for subjects with both baseline and post-baseline values. Shifts with respect to normal ranges and number and percentage of notable abnormalities will also be summarized.

Clinical notable vital sign values:

- Sitting pulse rate

- < 50 bpm and 25% decrease from baseline
- > 100 bpm and 25% increase from baseline
- systolic blood pressure
  - < 90 mmHg
  - $\geq$  140 mmHg
- diastolic blood pressure
  - < 60 mmHg
  - $\geq$  90 mmHg

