## Protocol Amendment 3 (08-Sep-2021)

### Amendment rationale

The purpose of this 3rd protocol amendment is to implement a change [REDACTED]

The introduced changes do not significantly impact patient safety, study population, trial conduct, or scientific value of the trial, and, therefore, are considered non-substantial.

Additionally, this change will not affect the Informed Consent.

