- **Section 9.1.1:** Following a request from health authorities to ensure that subjects who do not benefit from study participation need to discontinue study treatment, the statement *“The investigator must discontinue study treatment for a given subject if, he/she believes that continuation would negatively impact the subject's well-being.”* has been further clarified.
- **Appendix 1:** Amendment of clinically notable heart rates to <50 bpm and >100 bpm, respectively, in line with amended exclusion criterion #6a (see above).

[REDACTED]

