### 12.4.1 Definition of primary endpoint(s)

The primary objective of this study is to investigate the long-term safety and tolerability of LOU064 in subjects with CSU.

The primary variables are: AEs/SAEs, ECGs, laboratory assessment, and vital signs, etc. Baseline for safety analysis is defined as the last measurement before the first dose of study medication in the treatment period of this extension study.

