### **Vital signs**

Analysis of the vital sign measurements using summary statistics for the change from baseline for each post-baseline visit will be performed. Shifts with respect to normal ranges and number and percentage of notable abnormalities will also be summarized.

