## 16 Appendices

### 16.1 Appendix 1: Clinically notable laboratory values and vital signs

The following specific criteria have been identified for this study. Should these criteria be met, a re-test must be done within 5 days after the first assessment. Discontinuation of the study treatment should be considered if the abnormal hematology parameter is confirmed:

Hemoglobin: < 10 g/dl

Platelets: < 75 000/mm^3

White blood cells: < 3 000/mm^3

Neutrophils: < 1 500/mm^3

For all other laboratory assessments, the central laboratory will flag laboratory values falling outside of the normal ranges on the central laboratory report (which the investigator should review and sign-off) and the investigator will report any values considered clinically significant in the eCRF.

Notable values for vital signs and change from baseline will be summarized.

Notable values are defined as follows: heart rate of < 50 and > 100 bpm; systolic blood pressure of < 90 and  $\geq$  140 mmHg; diastolic blood pressure of < 60 and  $\geq$  90 mmHg.

For ECGs a notable QTc value is defined as a QTc (Fridericia's) interval of greater than 450 msec for males or greater than 460 msec for females – all such ECGs will be flagged by the central CRO's cardiologist and require assessment for clinical relevance by the investigator.

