**Document History – Changes compared to previous final version of SAP**

Date	Time point	Reason for update	Outcome for update	Section and title impacted (Current)
9- Sep- 2019	Prior to FPFV	Creation of final version	First version	NA
Jun- 2021	[REDACTED]	Protocol amendment v2.0  Address comment from dry-run review  Update the analysis visit window for eDiary assessment		Section 2.1.1.3 Update the assessment window for eDiary assessment (i.e. UAS7, [REDACTED]);  Section 2.3.2 Add baseline characteristics;  Section 2.5.1.1 Update the treatment emergent adverse event definition; Drop Table 2-2;  Section 2.5.1.2 Update the CTCAE grade definition in Table 2-3  Section 2.5.1.3 Update the notable abnormality criterion in ECG;  Section 2.5.1.4. Update the notable abnormality criterion in vital signs;  Section 2.6.3 Drop the handling rule for duplicated UPDD entries;  Section 2.13 text updated for more clarity on population included for IA2
Oct- 22	Prior to final analysis	Update for protocol deviation		Additional details added to Section 2.3.1 for protocol deviation analysis

Date	Time point	Reason for update	Outcome for update	Section and title impacted (Current)
		Updates for demog and baseline characteristic		More details are added to clarify that sex, race and ethnicity collected from core study.
		Medical History		Urticaria related medical history summaries added
				Medical history and current medical condition listings are added
		Study treatment/compliance		More details are added for calculations of exposure (weeks), exposure (years) and exposure (100 subject years)
		Section 2.4.2		Concomitant surgeries, medical procedures and non-drug therapies added
				Listing for Prior and concomitant medication included

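### The SAP counts a pulse below 50 or above 100 bpm as notable only with a 25% change from baseline, a condition absent from protocol Appendix 1 and not declared in SAP section 4

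*SAP*

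**What the plan says.** **Protocol.** Section 12.4.1 makes vital signs part of the primary safety analysis: "The primary variables are: AEs/SAEs, ECGs, laboratory assessment, and vital signs, etc". Its vital signs paragraph then plans the summary: "Shifts with respect to normal ranges and number and percentage of notable abnormalities will also be summarized". Table 8-9 states that vital signs are blood pressure and pulse and refers to section 16.1 for what is notable. Section 16.1 (Appendix 1) gives the definition: "Notable values are defined as follows: heart rate of < 50 and > 100 bpm". No change from baseline is part of it. The appendix does say that change from baseline will be summarized, but as a separate item.

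**SAP.** Section 2.5.1.4 plans the same summary with its own list. A sitting pulse under 50 is notable only with the added condition "bpm and 25% decrease from baseline", and one over 100 only with "bpm and 25% increase from baseline". The blood pressure limits in the same list match Appendix 1 and carry no change condition.

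**Record of the change.** The Jun-2021 row of the SAP document history has the entry "Update the notable abnormality criterion in vital signs". It does not describe the change. The reasons in that row cover the whole revision: protocol amendment v2.0, dry-run review comments and the eDiary window. The Oct-22 row does not mention vital signs. SAP section 4, the place for departures from the protocol's analyses, is marked as not applicable, and SAP section 1 says the data will be analyzed according to protocol section 12.

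**The concern.** Two current documents define the same summary differently, and the section meant to disclose such differences says there are none. A programmer following the SAP will not produce the count the protocol planned. A reader who relies on section 4 will take the pulse table to show everyone who went below 50 or above 100 bpm.

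The study has one arm and no hypothesis test, so descriptive counts are the primary result and their definitions carry the weight. The added condition works unevenly. It is hardest to meet on the low side for subjects who start low and on the high side for those who start high. Exclusion criterion 6a admits subjects with an ECG heart rate from 50 bpm. A subject who starts in the 50s and drops into the 40s is notable under Appendix 1 and mostly not under the SAP. Cardiovascular risk is one of the potential risks named in protocol section 4.5.

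**Working it through.** **1. The two rules.** Let B be the baseline pulse and P a later value, and read 25% as at least 25%.

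- Protocol: notable if P < 50 or P > 100.
- SAP: notable if (P < 50 and P ≤ 0.75 × B) or (P > 100 and P ≥ 1.25 × B).

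Every value that meets the SAP rule also meets the protocol rule, so the SAP count is at most equal to the protocol count. The two are equal only if every subject counted by the protocol rule also has a value that meets the 25% condition.

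**2. Where the rules part.**

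- P = 49 counts under the SAP only if B ≥ 49 / 0.75 = 65.3.
- P = 45 counts only if B ≥ 45 / 0.75 = 60.
- B = 50 requires P ≤ 0.75 × 50 = 37.5.
- P = 101 counts only if B ≤ 101 / 1.25 = 80.8.
- B = 90 requires P ≥ 1.25 × 90 = 112.5.

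In whole beats per minute:

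| Baseline | Protocol low | SAP low | Protocol high | SAP high |
|---|---|---|---|---|
| 50 | ≤49 | ≤37 | ≥101 | ≥101 |
| 55 | ≤49 | ≤41 | ≥101 | ≥101 |
| 60 | ≤49 | ≤45 | ≥101 | ≥101 |
| 65 | ≤49 | ≤48 | ≥101 | ≥101 |
| 66 to 80 | ≤49 | ≤49 | ≥101 | ≥101 |
| 85 | ≤49 | ≤49 | ≥101 | ≥107 |
| 90 | ≤49 | ≤49 | ≥101 | ≥113 |
| 100 | ≤49 | ≤49 | ≥101 | ≥125 |

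The rules agree for baselines of 66 to 80. They differ on the low side at 65 or less and on the high side at 81 or more. These results need no assumption beyond the reading of 25%.

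**3. One visit, illustrative.** Assume later values are normal around the subject's baseline with SD 8 bpm, in whole beats with continuity correction.

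- Baseline 55, low: protocol Φ((49.5 − 55)/8) = 0.246; SAP Φ((41.5 − 55)/8) = 0.046.
- Baseline 90, high: protocol 1 − Φ((100.5 − 90)/8) = 0.095; SAP 1 − Φ((112.5 − 90)/8) = 0.0025.

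**4. Whole treatment period, illustrative.** The documents give no pulse distribution, so one is assumed. Each subject has a true mean pulse drawn from a normal distribution with mean 72 or 75 and between-subject SD 10 or 12. The baseline and each later value add independent within-subject error with SD 7 or 10. Measured baseline is at least 50, and there are eight post-baseline visits (Weeks 4, 8, 12, 16, 20, 28, 40 and 52). This gives eight combinations, with 400,000 subjects simulated in each. Share of protocol-notable results that the SAP rule keeps:

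| | Below 50 | Above 100 |
|---|---|---|
| Subjects with any such value | 48–73% | 15–46% |
| Single values | 35–64% | 7–36% |

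The shares move with the assumptions. Without the baseline floor of 50, the share of low subjects kept is about 39–65%. With a within-subject SD of 5, it is about 20% for low and at most 5% for high, which is a larger loss.

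**The case against.** The best case for the plan has five parts.

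- **Small consequence.** The table is descriptive, there is no comparator, and the endpoint named in protocol Table 2-1 is adverse events. This is fair. It limits the severity but does not reconcile the definitions.
- **Other outputs cover it.** Change summaries, shift tables and ECG heart-rate tables are planned, and clinically significant findings are recorded as adverse events. However, the SAP prints no normal range for pulse and no cut-off for ECG heart rate, so none of these can be shown to supply the counts below 50 and above 100.
- **The change is not hidden.** The rule is printed in full in SAP 2.5.1.4, and the history logs an update with general reasons. This stands in part: the change is logged, but it is neither described nor specifically justified, and section 4 says there is none. The history does not prove that the 25% clause was what was added in Jun-2021, and the point does not depend on that. Nor does it depend on protocol Amendment 3 (08-Sep-2021), which postdates that row and leaves the absolute limits in place; its substance is redacted.
- **The simulated shares are soft.** This stands. They depend on assumed variability, the floor of 50 borrows an ECG entry criterion for sitting pulse, and the model has no drug effect. They show how much the definition matters, not that a signal would be missed.
- **A combined rule is sensible.** A limit joined to a change can be defended because it screens out subjects already near the limit. The fault is that it replaces the protocol's definition without being declared.

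**Conclusion.** The point holds. The current SAP and the current protocol define notable pulse differently, and SAP section 4 wrongly reports no change to the protocol's analyses. The SAP count cannot exceed the planned count and will fall below it whenever a subject moves past a limit without a 25% change at any such value.

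The threshold arithmetic is exact once 25% is read as at least 25%. The 48–73% and 15–46% shares rest on assumed pulse distributions and are illustrative only. No test, sample size or treatment rule is affected. This should be corrected because it changes what is reported for the primary safety objective, but it does not threaten the study's validity.

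**What to change.** In SAP section 2.5.1.4, tabulate the number and percentage of subjects with pulse below 50 bpm and with pulse above 100 bpm as Appendix 1 defines them. Keep the version with the 25% change as clearly labelled additional rows, and state whether 25% means at least 25%. A newly occurring version can be added if wanted. Record the added criterion in SAP section 4 with its reason.

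Declaring the change in section 4 alone would cure the disclosure fault, but it would still leave the protocol's planned count unreported. Showing both versions settles both.

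The cost is a few table rows and one SAP entry, with no new data. The drawback is that more pulses will be flagged, some of them benign; the labelled 25% rows let the reader separate these.

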### **2.5.2 Statistical hypothesis, model, and method of analysis**

No hypothesis testing is planned for the primary objective.

### **2.5.3 Handling of missing values/censoring/discontinuations**

Not applicable.

### **2.5.4 Supportive analyses**

Not applicable.

## **2.6 Analysis of the Secondary objective**

### **2.6.1 Secondary endpoint**

#### **UAS7 score change from baseline at Week 4 and over time**

Summary statistics for the absolute value, change and percent change from baseline in UAS7 will be presented for treatment period on SAF.

Summary statistics for the absolute value, change and percent change from baseline in HSS7 will be presented for treatment period on SAF.

Summary statistics for the absolute value, change and percent change from baseline in ISS7 will be presented for treatment period on SAF.

#### **Controlled disease (UAS7 $\leq$ 6) at Week 4 and over time**

The number and percentage of subjects achieved well controlled disease (UAS7 $\leq$  6) will be summarized for treatment period on SAF

provided.

Figure will be

#### **Complete clinical response (UAS7 = 0) at Week 4**

The number and percentage of subjects achieved complete clinical response (UAS7=0) will be summarized on SAF. [REDACTED]

## **2.6.2 Statistical hypothesis, model, and method of analysis**

Not applicable.

## **2.6.3 Handling of missing values/censoring/discontinuations**

The UAS7 is the sum of the average daily UAS over 7 days (range from 0 to 42). Note that the weekly score is derived according to the analysis week defined in [Table 2-1](#).

If one of the morning or evening score for HSS and ISS is missing, then the non-missing score for that day (morning or evening) will be used as the daily score. If one or more of the daily scores are missing, then the following principles will be applied to handle the missing data:

- The weekly Urticaria Activity Score is the sum of both the HSS7 score and the ISS7 score and will be missing if at least one of them is missing.
- If a patient has at least 4 non-missing daily scores within the 7 days, then the weekly score for HSS or ISS will be calculated as the sum of the available eDiary scores of that week, divided by the number of non-missing days multiplied by 7.
- If there are less than 4 non-missing daily scores within the 7 days, then the weekly score for HSS or ISS will be missing for that week. Accordingly, no UAS7 can be calculated.

### **Non-responser imputation method**

Missing values for binary response such as UAS7 = 0 response, UAS7 <= 6 response [REDACTED] in the secondary [REDACTED] analyses will be imputed by non-responder imputation method regardless of the reason for missingness.

For continuous variables such as UAS7 score, HSS7 score, ISS7 score, summary will be based on as observed data.

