## 2 Objectives and endpoints

Table 2-1 Objectives and related endpoints

Objective(s)	Endpoint(s)
Primary objective(s)	Endpoint(s) for primary objective(s)

To assess the long-term safety and tolerability of LOU064 in patients with CSU who have participated in CLOU064A2201.

	

Safety endpoints will include but not be limited to: occurrence of treatment emergent (serious and non-serious) adverse events during the extension study

Secondary objective(s)	Endpoint(s) for secondary objective(s)

To evaluate the efficacy of LOU064 when given without H1-antihistamines in patients with CSU who have participated in CLOU064A2201 with respect to change from baseline in UAS7, achieving controlled disease (defined by a UAS7≤6), and achieving complete response (defined by a UAS7=0) at Week 4 of treatment

To evaluate the long-term efficacy of LOU064 in patients with CSU who have participated in CLOU064A2201 with respect to maintaining or achieving controlled disease (defined by a UAS7≤6) over time

To evaluate the long-term efficacy of LOU064 in patients with CSU who have participated in CLOU064A2201 with respect to change from baseline in UAS7 over time

	

Change from baseline in UAS7 at Week 4

UAS7≤6 response at Week 4

UAS7=0 response at Week 4

UAS7≤ 6 response over time

Change from baseline in UAS7 over time

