### 3 Study design

[figure not shown]
This study is an open-label, single arm, multicenter, long-term safety and tolerability extension study for CSU patients rolling-over from CLOU064A2201. It consists of three periods ([Figure 3-1](#)):

- ***Observational period:*** Subjects rolling over from CLOU064A2201 with  $UAS7 < 16$  after the follow-up period at Week 16 will be further followed up without receiving LOU064 for up to 12 weeks. After relapse ( $UAS7 \geq 16$  at least once), the observational period can be terminated immediately at any time during these 12 weeks and subjects may enter the treatment period. Continuation of background therapy with an H1-antihistamine is at the discretion of the investigator; however, background therapy should only be interrupted in subjects with controlled CSU (e.g.  $UAS7 \leq 6$ ). Subjects who have never relapsed within 12 weeks will discontinue the study after the observational period.
- ***Treatment period:*** Subjects will be treated with 100 mg LOU064 bid for 52 weeks. Until Week 4 of treatment, no background medication with H1-antihistamines is permitted. After Week 4, subjects may start a background therapy with H1-antihistamines if deemed necessary by the investigator.
- ***Follow-up period:*** Treatment-free follow-up period following the treatment period. The minimum duration of treatment-free follow-up is 4 weeks for all subjects who stop treatment with LOU064 (either after completing the treatment period or after an early discontinuation of study treatment). Subjects who have a  $UAS7 \leq 6$  at Week 52 of the treatment period will extend their follow-up period until relapse ( $UAS7 \geq 16$ ) for up to a total of 16 weeks.

Rescue therapy to treat unbearable symptoms of urticaria on a day-to-day basis with an H1-antihistamine will be allowed throughout the study. A post-trial access program (which may be another extension study or a managed access program) for subjects who complete this study is under consideration.

**Figure 3-1** Study design

 Only when UAS7<16 at Week 16 of CLOU064A2201: Treatment-free observational period for up to 12 weeks. After relapse (UAS7 $\geq$ 16 at least once), subjects may immediately initiate treatment period. Subjects who have never relapsed within 12 weeks will discontinue the study after the observational period.

[figure not shown]

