 The minimum duration of the follow-up period will be 4 weeks for all subjects who stop treatment with LOU064. Subjects who achieve a UAS7 $\leq$ 6 at Week 52 of the treatment period will extend their follow-up period until they relapse (UAS7 $\geq$ 16). Follow-up will stop at Week 68 for all subjects.

 Background therapy is a second generation H1-antihistamine at a locally approved licensed posology given with a stable treatment regimen. Administration/discontinuation of the background H1-antihistamine is at the discretion of the investigator. Background therapy must not be taken from Day 1 until Week 4 of the Treatment period. It may be re-initiated at Week 4 if deemed necessary.

 Rescue therapy is a second generation H1-antihistamine at a locally approved licensed posology that is eliminated primarily via renal excretion (e.g. cetirizine, levocetirizine or bilastine). The rescue H1-antihistamine must differ from the background H1-antihistamine and may only be given to treat unbearable symptoms (itch) of CSU on a day-to-day basis.

Subjects rolling over from CLOU064A2201 will be assigned to one of the periods as follows (Figure 3-2):

- Subjects with a UAS7 $\geq$ 16 at Week 12 or Week 16 will directly enter the treatment period.
- Subjects with a UAS7 < 16 at Week 12 will not rollover into the extension study but enter the follow-up period of the core study CLOU064A2201.
- Subjects with a UAS7<16 at Week 16 (i.e., who have not relapsed during the follow-up period of CLOU064A2201) will be assigned to the observational period.

**Figure 3-2** Patient flow from CLOU064A2201

 Only subjects with a UAS7 ≥ 16 at Week 12 of CLOU064A2201 are eligible to directly rollover into the extension study CLOU064A2201E1 (and directly start with the treatment period). Subjects with a UAS7 < 16 enter the follow-up period of CLOU064A2201.

 After relapse (UAS7 ≥ 16 at least once), the observational period can be terminated immediately and subjects may enter the treatment period. Subjects who have never relapsed within 12 weeks will discontinue the study after the observational period.

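### Mean UAS7 over time is summarised as observed, although early stoppers before about Week 48 have no scheduled Week 52 value; a lesser point is that no visible text ties rescue use to the Week 4 results

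*SAP*

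**What the plan says.** **Means over time.** SAP 2.6.3 states: "For continuous variables such as UAS7 score, HSS7 score, ISS7 score, summary will be based on as observed data". Missing binary responses, by contrast, "will be imputed by non-responder imputation method regardless of the reason for missingness". SAP 2.1 shows N beside each continuous summary.

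**Early stoppers.** SAP 2.1.1.3 names a treatment policy strategy and places diary data collected after discontinuation into the study-day windows of SAP Table 2-1. It only suggests that collection and gives no end date. Protocol 9.1.1 lists lack of response among the reasons to stop treatment, and schedules an end-of-treatment visit followed by the Study Completion Visit 4 weeks later. Under the footnotes to Protocol Table 8-1, only subjects who complete treatment with UAS7<=6 are followed for longer.

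**Week 4.** The objective in Protocol section 2 is "efficacy of LOU064 when given without H1-antihistamines in patients with CSU who have participated in CLOU064A2201". The notes to Figure 3-1 in Protocol section 3 say "Background therapy must not be taken from Day 1 until Week 4 of the Treatment period". The same section says "Rescue therapy to treat unbearable symptoms of urticaria on a day-to-day basis with an H1-antihistamine will be allowed throughout the study", and limits rescue in that it "may only be given to treat unbearable symptoms (itch) of CSU on a day-to-day basis". Protocol 6.2.1 describes Day 1 to Week 4 as monotherapy without H1-antihistamines. SAP 2.6.1 defines the results by score: "The number and percentage of subjects achieved well controlled disease" (UAS7<=6) and "The number and percentage of subjects achieved complete clinical response (UAS7=0) will be summarized on SAF". SAP 2.4.2 tabulates rescue medication by ATC code and preferred term.

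**The concern.** An as-observed mean at a late visit describes the subjects who still supply a diary. If those who leave are the ones doing badly, the mean improves through selection. If those who stop lose the effect, the mean also misses that loss, although it belongs in the treatment policy value that the SAP names. N shows how many subjects are missing, but not what their absence does to the mean. Long-term change in UAS7 is a named secondary endpoint, so the Week 52 figure is likely to be quoted.

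The Week 4 matter is smaller. Non-responder imputation is triggered only by a missing score. A subject who took a rescue H1-antihistamine during Days 22-28 and recorded UAS7<=6 is therefore counted as a responder under an objective worded as efficacy without H1-antihistamines. Such a subject's score also enters the Week 4 mean change.

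**Working it through.** **1. Windows.** Week k covers Days 7k-6 to 7k. Week 52 is then Days 358-364, as in SAP Table 2-1. The visit day is 7 x 52 + 1 = 365, and 365 + 28 = 393, as in Protocol Table 8-1.

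**2. Cut-off.** SAP 2.6.3 needs at least 4 of 7 daily scores, so the diary must reach the fourth day of the window. With scheduled follow-up ending 28 days after the end-of-treatment visit (EoTV):

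| Visit | Window (days) | Diary must reach | Earliest EoTV that gives a score |
|---|---|---|---|
| Week 28 | 190-196 | Day 193 | 193 - 28 = Day 165 |
| Week 40 | 274-280 | Day 277 | 277 - 28 = Day 249 |
| Week 52 | 358-364 | Day 361 | 361 - 28 = Day 333 |

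Day 333 is Week 47.6 (333/7). Stopping in the first 332 of 364 days (91.2%) leaves no scheduled Week 52 score. This uses nominal visit days, with the EoTV on the day of the last dose. If the EoTV is 7 days late and the diary runs 30 days beyond it (assumed), the earliest last dose is 361 - 7 - 30 = Day 324, or Week 46.3.

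**3. Effect on the mean.** Let d be the share missing. The full mean change is (1-d) x observed + d x missing, so the overstatement of benefit is d x (mean change of missing - mean change of observed). With assumed d of 10-30% and an assumed gap of 5-15 points, this runs from 0.10 x 5 = 0.5 to 0.30 x 15 = 4.5 points.

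**4. Simulation, all inputs assumed.** n = 230 and 400 runs; baseline N(28, 7) bounded to 16-42; mean change -16 before the 0-42 bounds; between-subject SD 9, within-subject SD 5; the protocol's eight visits from Week 4 to Week 52; stopping depends on the current observed UAS7. Entries in the last three columns are UAS7 points of overstated benefit at Week 52.

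| Stopping per visit at UAS7>=16 / below 16 | Missing at Week 52 | As observed, stopping does not change UAS7 | As observed, stoppers return to baseline | MAR estimate, stoppers return to baseline |
|---|---|---|---|---|
| 5% / 0% | 12% | 0.71 | 1.85 | 1.14 |
| 10% / 0% | 21% | 1.41 | 3.42 | 2.03 |
| 5% / 3% | 23% | 0.32 | 3.52 | 3.22 |
| 10% / 3% | 32% | 1.03 | 5.15 | 4.13 |

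- A repeat run of the third column gave 0.71, 1.40, 0.31 and 1.04.
- With stopping driven by the next, unseen value, that column becomes 0.77, 1.48, 0.30 and 1.10.
- With equal stopping of 3% or 6% at all UAS7 levels, it is 0.00.
- Where stopping does not change UAS7, the MAR estimate is off by at most 0.01 if stopping depends on observed UAS7, and by 0.05 to 0.26 if it depends on the unseen value.
- The Week 52 UAS7<=6 rate with missing as non-response is 25-31%, against 31% in the full cohort, so it is not inflated.

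**5. Week 4.** At the roughly 250 subjects of Protocol 12.8.1, each reclassified responder moves a rate by 1/250 = 0.40 points (more if the SAF is smaller).

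- Reading unbearable itch as a score of 3, one such half-day adds 3/2 = 1.5 to UAS7. A fully scored week at UAS7<=6 can hold 6/1.5 = 4 of them, provided there are no hives and no other itch. With hives also at 3, it holds 6/3.0 = 2.
- UAS7=0 is exposed mainly through partly scored weeks, because four days with one entry each (4 of 14 entries) suffice.
- If 30-40% reach UAS7<=6 and 5-20% of them took rescue in Days 22-28 (both assumed), the rate falls by 0.30 x 0.05 = 1.5 to 0.40 x 0.20 = 8 points. It falls by zero if no responder took rescue.

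**The case against.** On the means, the plan is not naive. It names a treatment policy strategy, uses retrieved data, shows N with quartiles, reports disposition, and counts missing as failure in UAS7<=6 over time. Plain summary statistics are what Protocol 12.5.1 specifies. An MAR estimate targets something close to what would have happened had subjects continued, which is not treatment policy, and the last column of the table shows how much it can leave uncorrected. This stands, and it is why an MAR estimate alone is not enough.

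A reader might infer that everyone who stops before Week 48 has no Week 52 value. The documents do not say so. The cut-off is inferred from the visit schedule, and SAP 2.1.1.3 sets no end date for diary collection, so sites could supply later data, although none is scheduled.

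On Week 4, Protocol section 3 bars background H1-antihistamines until Week 4, allows rescue throughout, and defines the two separately. A reader might infer that the Week 4 rates are invalid. If the objective means only no background H1-antihistamine, they are legitimate. The assumed share of responders taking rescue has no source in the documents, and zero is equally compatible with them.

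Finally, text is redacted beside the Week 4 and non-responder paragraphs. The SAP document history also cites a Section 2.13 beyond the visible sections. A rule or analysis may exist there, so only the absence of visible text can be claimed.

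**Conclusion.** The main point holds: followed as visible, the plan lets late mean changes in UAS7 describe mainly the subjects who stayed, and the scheduled follow-up of early stoppers is too short to prevent this. That the means will actually overstate benefit is not established. It requires that poor responders leave or that stoppers lose the effect, and the size is unknown. The 0.3 to 1.5 points, and the 1.9 to 5.1 points if stoppers return to baseline, are illustrations on assumed inputs. UAS7<=6 over time is not affected in this direction.

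The Week 4 point is secondary: how rescue users count is not visibly stated, so the results should not be read as H1-antihistamine-free efficacy without further support.

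Both are minor. The endpoints are secondary, the study is single-arm and descriptive, and no error rate or sample size changes.

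**What to change.** Keep every planned table and add the following in SAP 2.6.3. If redacted sections already contain these analyses, a cross-reference is enough.

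1. **Mean UAS7 change by visit, all SAF subjects, retrieved drop-out data included.** Give two supportive versions. The first is under MAR (MMRM or multiple imputation), labelled as close to what would have been seen had subjects continued. The second sets values missing after stopping back to baseline. The two bracket the treatment policy value provided that stoppers' true course lies between keeping the benefit and losing all of it.

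2. **Week 4.** State how rescue use is handled, and label the planned results as without background H1-antihistamine if that is the intended meaning. Beside them, show UAS7<=6 and UAS7=0 with recorded H1-antihistamine intake counted as non-response, once for intake in Days 22-28 and once for any intake in Days 1-28. Show the Week 4 mean change with and without subjects who have recorded intake. Use recorded dates, not those imputed under SAP 5.1.3, and report how many records are partial or open-ended.

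3. **Protocol wording.** Protocol 6.2.1 must be reconciled with sections 3 and 6.2.3 on H1-antihistamine use before Week 4.

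The cost is SAP wording and a few tables. They draw on the diary and on medication records that Protocol 6.2.1 already requires. The drawbacks are untestable assumptions and possibly less favourable figures. No visible text requires a date for each as-needed dose, so intake may be over- or under-captured; the tables should say so.
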